3.2. Statistical significance and confidence interval

We will consider a p-value < 0.05 as statistically significant, and therefore we will present 95% confidence intervals.

3.3. Adherence and protocol deviations

Any deviations from the protocol and this analysis plan will be described in the subsequent manuscript where the results of the study are presented.

4. Study populations

4.1. Eligibility

- 4.1.1. Inclusion Criteria
 - Age ≥16 years
 - Admitted to an adult, general ICU in England or Wales as an emergency (i.e. unplanned)
 - Admitted to ICU for either:
 - \circ $\,$ confirmed COVID-19 between 1st January to 1st July 2020 $\,$
 - without confirmed COVID-19 between 1st July 2016 and 1st July 2020 (patients admitted prior to 2020 are included to account for seasonal variation and identify specific impacts of the pandemic on patient follow-up)

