6. OBJECTIVES AND OUTCOME MEASURES

Objectives	Outcome Measures	Timepoint(s) of evaluation of this outcome measure (if applicable)

Primary Objective
 
To estimate the risk of death for patients who survived to hospital discharge after treatment on an ICU for COVID-19 and compare these risks to patients treated on ICU as an emergency for other conditions
	
Primary outcome
 
 • Death as recorded in the Civil Registration -- Deaths 	
1 year after discharge from ICU

Secondary Objectives
 
To estimate the risk of adverse events for patients who survived to hospital discharge after treatment on an ICU for COVID-19 and compare these risks to patients treated on ICU as an emergency for other conditions
	
Secondary outcomes
 
 • Emergency hospital admission • Emergency hospital admission for respiratory infection • Emergency hospital admission for a major adverse cardiac event (myocardial infarction, stroke, heart failure) • Emergency hospital admission for a venous thrombotic event (deep 	
180 days after discharge from ICU AND 1 year after discharge from ICU

	vein thrombosis or pulmonary embolism) 
 • Development of end stage renal failure treated by renal replacement therapy 	

Exploratory Objectives
 
To compare the risks in patients treated in ICU for COVID-19 to patients who survived to hospital discharge after treatment on an ICU for other bacterial or viral respiratory infections during the same period (January to June 2020)
 
To compare the risks in pregnant patients treated in ICU for COVID-19 with an age-matched control group
	
Primary outcome
 
 • Death as recorded in the Civil Registration -- Deaths 
Secondary outcomes
 
 • Emergency hospital admission • Emergency hospital admission for respiratory infection • Emergency hospital admission for a major adverse cardiac event (myocardial infarction, stroke, heart failure) • Emergency hospital admission for a venous thrombotic event (deep vein thrombosis or pulmonary embolism) • Development of end stage renal failure treated by renal replacement therapy 	180 days after discharge from ICU AND 1 year after discharge from ICU

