11.4. Analysis populations

Primary group

Our primary group will be patients admitted with confirmed COVID-19 between 1st January to 1st July 2020.

Comparator groups

The primary comparator group will be patients admitted to ICU with viral or bacterial pneumonia between 1st July 2016 and 1st July 2019.

Secondary comparator groups will include:

- All emergency ICU admissions between 1st July 2016 and 1st July 2019
- All emergency ICU admissions between 1st July 2016 and 1st January 2020 where the primary diagnosis was not COVID-19
- All emergency ICU admissions between 1st January and 1st July 2020 where the primary diagnosis was not COVID-19

Pregnant patients

We will undertake a sub-group analysis in patients who were pregnant when treated for COVID-19 on ICU between 1st January and 1st July 2020.

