4.4. Cohort definitions

4.4.1. Patients with confirmed COVID-19 between 1st January to 1st July 2020 This group will consist of all individuals who were admitted to an intensive care unit between 1st January and 1st July 2020 with a confirmed diagnosis of COVID-19.

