4.4.4. Non-COVID ICU admissions 1st January 2020 – 1st July 2020

All emergency ICU admissions between 1st January 2020 and 1st July 2020 where the primary diagnosis was not COVID-19. This cohort includes patients admitted to ICU concurrently to the primary COVID-19 cohort. While this cohort will likely be small, it will possibly provide a fairer comparison of outcomes if the pandemic did affect the healthcare provision during follow-up (i.e. if there were a reduction in the number of hospital admissions for non-Covid causes during the period of the pandemic due to restrictions).

5. Analysis

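### Neither rule that defines the January–July 2020 comparator removes unrecognised COVID-19 recorded under another diagnosis, and matching may enrich it

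*SAP*

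**What the plan says.** Protocol 8.2 and SAP 4.1.1 divide eligible admissions in two: those for confirmed COVID-19 in January–July 2020, and those "without confirmed COVID-19 between 1st July 2016 and 1st July 2020". The COVID-19 cohort in SAP 4.4.1 is made up of ICU patients "with a confirmed diagnosis of COVID-19". Neither document defines confirmation or asks for a negative test in 2020 comparators. The only listed exclusion is death in hospital.

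The concurrent comparator carries a second rule. SAP 4.4.4 defines it as "All emergency ICU admissions between 1st January 2020 and 1st July 2020 where the primary diagnosis was not COVID-19", and Protocol 11.4 lists the same group among its secondary comparators. SAP 4.4.4 says of this cohort that "it will possibly provide a fairer comparison of outcomes" if the pandemic changed care during follow-up, and cautions: "While this cohort will likely be small".

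An exploratory objective (Protocol 6, SAP 1.2) compares COVID-19 patients with survivors of treatment on an "ICU for other bacterial or viral respiratory infections during the same period (January to June 2020". Neither SAP 4.4 nor Protocol 11.4 gives a cohort definition for that group.

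The protocol's main comparison is elsewhere: "The primary comparator group will be patients admitted to ICU with viral or bacterial pneumonia between 1st July 2016 and 1st July 2019".

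Matching (SAP 5.4.3) is one-to-one, at first greedy nearest neighbour, on a score built from the SAP 5.2 covariates. These include month, region, severity score, and length of ventilation and organ support. Admission diagnosis is not among them. The only sensitivity analysis in SAP 5.6 is multivariable regression.

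**The concern.** In the first half of 2020 some ICU patients with COVID-19 may have been untested, or tested negative, and recorded under another diagnosis. The plan does not say where they belong. If they sit in the comparator, the contrast partly sets COVID-19 against COVID-19.

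This matters because the concurrent cohort has a specific job. The 1 July 2019 cut-off in SAP 4.4.2 secures only six months of follow-up before the pandemic, while the primary outcome is at one year. The 2020 cohort is the one that shares pandemic conditions with the COVID-19 patients. If its contrast came out smaller than the historical one, a reader could credit changed healthcare provision when the cause was dilution, and the plan has no analysis that would tell the two apart. Regression adjustment cannot repair a wrong cohort label.

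**Working it through.** **Step 1. Where each kind of patient goes, on the literal wording (January–July 2020)**

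| Patient | COVID-19 cohort (SAP 4.4.1) | 2020 comparator (SAP 4.4.4) |
|---|---|---|
| Confirmed, primary diagnosis COVID-19 | in | out |
| Confirmed, other primary diagnosis | in | in, on 4.4.4 alone |
| Unconfirmed, primary diagnosis recorded as COVID-19 | out | out |
| Unconfirmed (suspected, untested or false negative), other primary diagnosis | out | **in** |

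The last row is the point. Rows two and three show that the two rules do not line up: one class can satisfy both cohort definitions, and another is eligible but falls in neither 2020 cohort.

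**Step 2. The plan's own figures**

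- 90,000 × 3.5 = 315,000, and 315,000 + 4,600 = 319,600, as stated in Protocol 11.3 and SAP 2.2.
- 90% of 5,000 is 4,500 rather than 4,600. This does not affect the shares below.
- The total contains no January–July 2020 non-COVID patients, so the comparator has no stated size. Half a year at pre-pandemic rates is 90,000 × 0.5 = 45,000. Since the SAP expects a small cohort, I used an assumed range of 15,000 to 45,000.

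**Step 3. Upper bound on contamination and dilution**

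Let f be the share of true COVID-19 survivors never confirmed. It is an assumption, because the documents give no value.

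- Missed survivors = 4,600 × f/(1 − f).
- Largest share c of 4,600 one-to-one controls = missed/4,600.
- With true risk ratio R, and missed cases at the same risk as confirmed ones, observed ratio = R/[1 + c(R − 1)].

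| f | Missed | Share of pool of 45,000 / 15,000 | Largest c | R = 1.5 seen as | R = 0.70 seen as |
|---|---|---|---|---|---|
| 5% | 242 | 0.5% / 1.6% | 5.3% | 1.46 | 0.71 |
| 10% | 511 | 1.1% / 3.4% | 11.1% | 1.42 | 0.72 |
| 20% | 1,150 | 2.6% / 7.7% | 25% | 1.33 | 0.76 |

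For example, at f = 10%: 1.5/(1 + 0.111 × 0.5) = 1.42. The bound supposes that every missed survivor is matched and that all 4,600 pairs are formed. If a comparator were smaller than 4,600, fewer pairs would exist and the share could be higher. The size of the respiratory infection group is not stated.

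**Step 4. Does matching enrich such patients?**

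I simulated greedy one-to-one nearest-neighbour matching without replacement on a normally distributed score. Confirmed and hidden COVID-19 patients had mean d and other comparators mean 0, all with SD 1. I used f = 5% and 10% and pools of 15,000, 30,000 and 45,000.

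| Separation d (SD) | Enrichment over pool share | Matched controls with COVID-19 | R = 1.5 seen as |
|---|---|---|---|
| 0.5 | 1.0–1.5 | 0.8%–3.9% | 1.49–1.47 |
| 1.0 | 1.8–2.8 | 1.5%–6.1% | 1.49–1.46 |
| 1.5 | 2.5–5.2 | 2.5%–8.6% | 1.48–1.44 |
| 2.0 | 2.9–7.1 | 3.7%–10.3% | 1.47–1.43 |

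Enrichment is near nil when the covariates separate the cohorts weakly and substantial when they separate them well.

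**Step 5. Power**

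At 4,600 per group, assumed 5% one-year comparator mortality and R = 0.70, power falls from 0.95 to 0.89 at c = 11% and 0.78 at c = 25%. At 10% or 15% mortality it stays at 0.97 or above. The main effect is bias, which sample size does not cure.

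**The case against.** The strongest reply has four parts.

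- **There is a second rule.** A reader might infer that comparator membership rests on confirmed status alone, so that any clinically diagnosed patient can enter. The documents do not support that. SAP 4.4.4 and Protocol 11.4 also use primary diagnosis, which keeps out an unconfirmed patient whose primary diagnosis is recorded as COVID-19. It does not keep out one recorded as, say, viral pneumonia, and it is not attached to the exploratory respiratory infection group.
- **Matching need not favour these patients.** A reader might infer that they are taken first as controls. Nearest-neighbour matching takes the closest control, not the highest-scoring one, and no matching order is stated. That hidden cases resemble confirmed ones on the covariates is plausible but is not in the documents. Enrichment is therefore conditional. The contamination does not depend on it.
- **Few contrasts are touched.** A reader might infer that all comparisons are attenuated. The protocol's primary comparator ends on 1 July 2019, and the cohorts in SAP 4.4.2 and 4.4.3 end by 1 January 2020. Only one secondary comparator and one exploratory objective are exposed. The SAP presents the 2020 cohort cautiously and uses several cohorts to check robustness. That is a partial check, but disagreement between cohorts could not be attributed to dilution rather than to a pandemic effect.
- **The data may not allow the filter.** The coding windows in Protocol 7.3 and 12.1 are five years before ICU admission and one year after hospital discharge, and neither names the index stay. Nor do the documents say that the Case Mix Programme holds a suspected-COVID or organism field. This stands, and it makes the fix conditional on a check.

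**Conclusion.** The gap is real but limited. As written, the plan can place unrecognised COVID-19 patients among the January–July 2020 comparators, and probably most of all in the undefined January–June 2020 respiratory infection group, where a missed case would most naturally be coded. Contrasts with those two groups would be biased towards no difference. The main comparison and the other pre-2020 cohorts are essentially unaffected.

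The size cannot be fixed from the documents. The 25% share and the ratio of 1.33 are extremes: they need one true case in five unconfirmed and every one of them matched. With 5% to 10% unconfirmed, the simulated ratios lie between about 1.49 and 1.43 for a true 1.5. All these figures assume that missed cases carry the same risk as confirmed ones, and they use risk ratios as a stand-in for the planned hazard ratios. This is a worthwhile, cheap improvement to secondary and exploratory comparisons, not a threat to the primary one.

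**What to change.** 1. In SAP 4.4.4, exclude patients with any confirmed, suspected or clinically diagnosed COVID-19 code in the index stay, using the Case Mix Programme or linked hospital data. First confirm that the extract covers the index stay.
2. Add a definition of the same-period respiratory infection group to SAP 4.4, with the same exclusion.
3. State what counts as confirmed and where suspected cases go, so that the 2020 cohorts are mutually exclusive. Keep the COVID-19 cohort as confirmed cases.
4. Add a sensitivity analysis that also drops March–July 2020 viral pneumonia with no organism identified, if that field is available.

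The cost is a diagnosis filter, one extra analysis and a check on the extract. The 2020 comparator, which the SAP already expects to be small, becomes somewhat smaller. The sensitivity analysis will also lose some genuine non-COVID pneumonia, the closest clinical comparison, which is why it should stay a sensitivity analysis.

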4.1.2. Exclusion Criteria

The participant may not enter the study if ANY of the following apply:

• Patients who died in hospital after treatment on an ICU

We chose to exclude ICU admissions after 1st July 2020 to account for a possible three-month delay in patient data being registered in hospital episode statistics (HES) and national audit databases. Linking data sources in July and October 2021 will maximise the chance that complete data will be available for outcomes at 180 and 365 days respectively.

4.2. Recruitment

Participants will be recruited from general adult ICUs across England and Wales who participate in the ICNARC CMP audit. All ICUs in England and Wales have participated in the CMP audit since 2015.

4.3. Withdrawal/follow-up

This is an observational study. Participants can request their data to be deleted at any time in accordance with GPDR and the study privacy policy. The number of participants who do withdraw their data will be summarised.

4.4. Cohort definitions

4.4.1. Patients with confirmed COVID-19 between 1st January to 1st July 2020 This group will consist of all individuals who were admitted to an intensive care unit between 1st January and 1st July 2020 with a confirmed diagnosis of COVID-19.

4.4.2. ICU admissions 1st July 2016 – 1st July 2019

All emergency ICU admissions between 1st July 2016 and 1st July 2019. The 1st July 2019 cut-off is intended to allow 6 months follow-up of all patients before the COVID-19 pandemic had opportunity to influence healthcare provision.

4.4.3. ICU admissions 1st July 2016 – 1st January 2020

All emergency ICU admissions between 1st July 2016 and 1st January 2020 where the primary diagnosis was not COVID-19. The cohort is the same as the previous one, with an additional 5 months' of ICU admissions. To allow for admissions which are closer in time to be included, and therefore to check the robustness of analyses involving the previous cohort.

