5.2. Assumed confounding covariates

The following variables are assumed to be related to the risk of experiencing one or more of the outcomes, and will therefore be included in the baseline characteristics table, be included as covariates in the multivariable regression models, and be included as covariates in the propensity scores.

- Patient demographics: age, sex, ethnicity, index of multiple deprivation (IMD), body mass index (BMI), clinical frailty score, smoking status, month of admission, dependency prior to ICU admission (fully/partial/total assistance with activities of daily living), geographical region
- Medical history: comorbidities (as per Elixhauser (14)), dialysis-dependent, total length of previous hospital admissions in year prior to ICU admission.
- Hospital/ICU stay characteristics: Length of hospital stay prior to ICU transfer, Length of ICU stay, length of hospital stay after discharge from ICU, hospital region, month of admission.
- Acuity: APACHE-II/ICNARC severity score at admission, length of mechanical ventilation, length of advanced organ support (cardiovascular, respiratory, renal, liver, neurological)

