5.4.3. Comparison of COVID-19 cohort to other cohorts using propensity score matching

For each comparison of the COVID-19 cohort to a non-COVID cohort we will use propensity score matching to create cohorts that are similar in terms of baseline characteristics and confounding variables. We will construct a propensity score using logistic regression where the outcome is the cohort status, and the covariates will be those previously defined in Section 5.2. The model will allow for non-linear relationships between continuous variables and the outcome. The propensity score will then be estimated for each patient. One to one matching will be performed based on the

propensity score, initially using a nearest neighbour (greedy) approach. We will assess the balance achieved through the matching process using standard approaches, such as Q-Q plots, and assessments of the absolute standardised mean difference. If the covariates are not well balanced after nearest neighbour matching, alternative approaches will be tested, such as full matching, until sufficient balance is achieved. If sufficient balance cannot be achieved or too many patients from the COVID cohort are removed by the matching algorithm, we will consider using the propensity score for inverse probability weighting in our Cox regression models.

Once matched cohorts have been identified, we will analyse the outcomes with the standard regression modelling as described in Section 5.4.2– using Cox regression for the death outcome, and competing risk approaches for the secondary outcomes. However, since the data will now be clustered due to the matching, we will need to account for this in the regression models. We will therefore use cluster-robust standard errors.

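### The matched analysis of cohort 4.4.3 cannot show whether more recent comparators change the 4.4.2 result, because its added July to December 2019 admissions fall outside the COVID-19 cohort's calendar months

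*SAP*

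**What the plan says.** SAP 4.4.2 defines a comparator as "All emergency ICU admissions between 1st July 2016 and 1st July 2019". SAP 4.4.3, like Protocol 11.4, moves the end date to 1 January 2020: "All emergency ICU admissions between 1st July 2016 and 1st January 2020 where the primary diagnosis was not COVID-19". The SAP describes the change as follows: "The cohort is the same as the previous one, with an additional 5 months' of ICU admissions". Its reason is: "To allow for admissions which are closer in time to be included, and therefore to check the robustness of analyses involving the previous cohort".

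The COVID-19 cohort (SAP 4.4.1) is everyone "admitted to an intensive care unit between 1st January and 1st July 2020 with a confirmed diagnosis of COVID-19".

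SAP 5.2 names month of admission twice, the second time in "length of hospital stay after discharge from ICU, hospital region, month of admission". All variables in that list are to "be included as covariates in the propensity scores". SAP 5.4.3 applies the score to every COVID-19 versus non-COVID comparison, with one-to-one matching on the "propensity score, initially using a nearest neighbour (greedy) approach". No caliper, no exact matching on month and no coding of month are given. Full matching and inverse probability weighting are fallbacks, and the target population for weighting is not stated.

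Each comparator also receives descriptive incidence (5.4.1), unadjusted models (5.4.2) and, as a sensitivity analysis, multivariable regression (5.6).

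**The concern.** Cohorts 4.4.2 and 4.4.3 differ only by the second half of 2019. The COVID-19 cohort lies in the first half of the calendar year. A propensity score that contains month gives the added patients a probability near zero, so matching passes over them. The patients who were meant to make the comparator more recent then hardly enter the matched analysis.

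SAP section 6 relies on different comparison cohorts, along with different methods, to check robustness. If the matched 4.4.2 and 4.4.3 results agree, a reader will naturally take it that a more recent comparator gives the same answer. The matched analysis could hardly have shown otherwise. Drift in outcomes before the pandemic would remain unexamined behind an apparently reassuring check.

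**Working it through.** **1. Length of the added block.** From 1 July 2016 to 1 July 2019 is 1,095 days, and to 1 January 2020 is 1,279 days. The difference is 1,279 − 1,095 = 184 days, July to December. The stated five months is not reproduced. The sample size is: 90,000 × 3.5 = 315,000, plus 4,600 = 319,600 (SAP 2.2). Its 3.5 years against the three of 4.4.2 also implies six months.

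**2. Size of the added block**, from the plan's 90,000 survivors a year:
- 4.4.2: 90,000 × 3 = 270,000
- added: 90,000 × 0.5 = 45,000
- share of 4.4.3: 45,000 / 315,000 = 14.3%; the other 85.7% is cohort 4.4.2.

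**3. Calendar overlap.** The COVID-19 months are January to June plus 1 July. The added months are July to December, plus 1 January if that end date is inclusive. They share 1 July and at most 1 January. With admissions spread evenly over the year (assumed), 4.4.2 already holds 3 × 45,000 = 135,000 January to June comparators, or 135,000 / 4,600 ≈ 29 per COVID-19 patient. Matching has no need of the added block.

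**4. Simulated matching.** The set-up was 4,600 COVID-19 patients, 270,000 + 45,000 comparators, a logistic score and greedy 1:1 matching without replacement on the logit, with no caliper. Assumed, not in the documents: the covariate distributions (age, severity, ventilation, sex), comparators uniform over months, and two COVID-19 month profiles. One profile peaks in March–April; the other is flat over January–June. Share of matched controls from July–December 2019:

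| Month in the score | Peaked | Flat |
|---|---|---|
| Categories | 0.13% | 0.11% |
| Spline | 0.00% | 0.20% |
| Cyclic | 0.04% | 2.46% |
| Linear | 3.87% | 3.85% |
| Left out | 14.67% | 14.43% |

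With month left out, the share returns to about the block's 14.3%, so month is the cause. Weighting to the COVID-19 population (ATT) gives the block at most 0.2% of comparator weight with categories or a spline. Weighting to the combined population (ATE) gives it about 14.1%.

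**5. Same pool, not the same estimate.** The 4.4.2 and 4.4.3 matched control sets overlapped by 45–67% (categories) and 25–39% (spline), because refitting the score re-selects among near-equivalent controls. With categories, the matched odds ratio moved from 1.008 to 0.970 (peaked) and from 1.035 to 1.121 (flat), although the added block supplied only about 0.1% of controls. Such differences are selection noise and say nothing about recency.

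**6. Analyses that keep everyone.** Suppose outcome rates were 20% higher in the added patients (hypothetical):
- Unadjusted, the pooled comparator rate changes by (270,000 + 45,000 × 1.2) / 315,000 = 1.029, or 2.9%.
- Matched with linear month, it changes by about 0.039 × 20% = 0.8%.
- Matched with categories or a spline, it changes by at most 0.002 × 20% = 0.04%.

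In the simulation the added patients were given a log-odds of death 0.1 higher. The unadjusted odds ratio moved from 1.010 to 0.996 (peaked) and from 1.070 to 1.053 (flat). The multivariable one moved from 0.991 to 0.986 and from 1.013 to 1.012, with a standard error of about 0.07 on the log scale. The multivariable shift is small because, once month is adjusted for as categories, August to December hold no COVID-19 patients and July holds only those of 1 July. Those strata inform the contrast almost only through the other coefficients.

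**The case against.** **The estimate is not fixed.** A reader might infer that the 4.4.3 result must reproduce the 4.4.2 result by construction. The documents do not support that. Matching is on the score rather than on month, and the coding of month is open. A linear term admits about 4% of controls from the added block and a cyclic term up to 2.5%. The matched sets differ even when the pool is effectively shared. This objection stands: the limitation concerns the control pool of the matched or ATT-weighted analysis.

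**Other analyses use the added patients.** This is true of the descriptive, unadjusted, multivariable and any ATE-weighted results, so 4.4.3 is not empty. They remain weak checks because 86% of the cohort is shared, and in the unadjusted case recency is mixed with season.

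**Recency is covered elsewhere.** A reader might infer that no cohort in the plan addresses closeness in time. Cohort 4.4.4 does: it is concurrent and same-season. It cannot, however, separate pre-pandemic drift from the pandemic effects that the SAP itself raises for it.

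**The aim is modest.** A nested, extended-window cohort is an ordinary sensitivity check, and the SAP never claims to isolate secular change. But its stated reason is closeness in time, and the matched analysis cannot speak to that.

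**Month might mean month and year.** SAP 4.1.1 ties pre-2020 admissions to seasonal variation, and Protocol 11.2 uses week of the year. Month and year would also separate every pre-2020 comparator from the COVID-19 cohort.

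**It is a secondary comparator.** This stands. Protocol 11.4 makes pneumonia admissions to July 2019 the primary comparator, and that result is unaffected.

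**Conclusion.** The point holds for the matched (or ATT-weighted) analysis of 4.4.3. That analysis uses effectively the January to June 2017–2019 controls already in 4.4.2 and cannot test whether more recent admissions matter. The added block, 14.3% of the cohort, supplies about 0 to 0.2% of matched controls with month as categories or a spline, and up to about 4% with a linear term.

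The dates, the 184 days and the 14.3% follow from the documents, the last given the plan's round 90,000 a year. The matched shares rest on assumed covariate and month distributions and on the unstated coding of month. The direction does not: the two periods share only boundary days.

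No planned 4.4.3 analysis is a sensitive, season-aligned test of pre-pandemic drift. This is a worthwhile and cheap improvement to a secondary robustness check. The five-month figure by itself is clerical.

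**What to change.** - Keep 4.4.3 for the descriptive, unadjusted and multivariable results. State that agreement between the matched 4.4.2 and 4.4.3 results is not evidence on recency.
- State how month is coded and, if weighting is used, the target population. Report how many matched controls come from July to December 2019.
- Add matched comparisons against 1 January to 1 July admissions of 2019, of 2018 and of 2017 separately, at 180 days and one year. Read whether the hazard ratio drifts as the comparator year nears 2020. The three share the same COVID-19 patients, so they should be read as a trend and not as independent tests.
- Correct five months to six in SAP 4.4.3.

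**Cost.** SAP wording and three further runs of a matching program that is needed anyway. All three groups already lie inside 4.4.2, so no new data are required. Each pool falls to about 45,000, or 45,000 / 4,600 ≈ 10 comparators per COVID-19 patient, so matches may be less close. Part of the 2019 group's one-year follow-up falls in 2020, which is why its 180-day result should be shown beside it. The yearly comparisons test drift up to mid-2019; they do not bring in the second half of that year.
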